#### 3. INTRODUCTION AND RATIONALE

The mainstay of antenatal treatment of fetal anemia due to red cell alloimmunization is (serial) intrauterine red cell transfusions (IUT). The mainstay of postnatal treatment in hemolytic disease of the fetus and newborn (HDFN) is (1) intensive phototherapy and exchange transfusion to treat hyperbilirubinemia and prevent kernicterus, and (2) top-up transfusions to treat anemia. Up to 80% of infants with HDFN treated with IUT require at least one top-up transfusion for late anemia during the first 3 months of life, with an average of two top-up transfusions and therefore two hospital admissions per infant. Late anemia is attributed to two mechanisms: "hyporegenerative anemia" characterized by depressed erythropoiesis and "late anemia of hemolytic disease" caused by persisting antibodies, destroying newly produced erythrocytes. "Hyporegenerative anemia" occurs in particular in neonates treated with several IUTs due to bone marrow suppression. To distinct these two mechanisms, a persistence of a high antibody titer can be used. Several risk factors for late anemia have been reported, including serial IUT (due to bone marrow suppression), severity of HDFN, reduced use of exchange transfusions during the neonatal period and reduced survival of transfused red blood cells. Finally, erythropoietin deficiency is also considered as a possible contributing factor to late anemia. Erythropoietin (EPO) has been increasingly used in neonates to prevent or reduce neonatal anemia without short or long-term adverse effects. Several small studies and casuistic reports suggest that neonates with HDFN may benefit from treatment with EPO to reduce the risk of delayed anemia and subsequent top-up transfusions. However, other authors found that EPO may be less effective than expected. Due to the lack of evidence, routine use of EPO is currently not recommended. To determine a role for EPO in this group of patients, a well-designed randomized controlled clinical trial of sufficient sample size is required. Potentially, EPO stabilizes the hemoglobin levels of these infants and thus prevents anemia, hospital admissions for top-up transfusions and potential transfusion reactions, creating a more stable and natural postnatal course for patients with HDFN. In this scenario, the current

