# Secondary end points:

- The percentage of infants requiring a top-up transfusion up to 3 months of life;
- Time form birth to first top-up transfusion (days);
- Number of days of admission for top-up transfusions;
- The percentage of infants with a systolic blood pressure ≥ 2 SD above age adjusted mean systolic blood pressure during treatment;
- The percentage of infants with ferritin levels >200 µg/L during treatment;

Exploratory end point:

Long-term neurodevelopmental outcome at 2 years of age using the BSID-III test.

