# 5.9 Cost-effectiveness

By calculating the costs of the intervention (EPO treatment), and taking into account

caregiver time and other services needed and the costs of top-up transfusions, we will assess the cost-effectiveness of the intervention compared to the standard of care. The total costs of EPO treatment using darbepoetin alfa are approximately 32 Euro (total of 8 vials of darbepoetin) per child. The costs of a clinical admission at a day-care-center for one top-up transfusion are approximately 700 Euros. An effective treatment with EPO will reduce the average rate of top-up transfusions from an average of 2 top-up transfusions per child to an average of 1 top-up transfusion per child (absolute reduction of 50%), hereby reducing the costs of treatment by almost 50%, from 1400 Euros (without EPO treatment) to 732 Euros (with EPO).

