#### 8.2 AEs, SAEs and SUSARs

#### 8.2.1 Adverse and serious adverse events (SAEs)

Adverse events are defined as any undesirable experience occurring to a patient during a clinical trial, whether or not considered related to the investigational drug. All adverse events reported spontaneously by the patient's parents or caregivers or observed by the investigator or his staff will be recorded. Serious adverse events are those which result in:

- Death
- A life-threatening event (i.e. an immediate risk of death)
- Hospitalization or prolongation of hospitalization;
- Severe/permanent disability.

During protocol treatment, all deaths, all SAE's that are life-threatening and any unexpected SAE must be reported to the study coordinator within 48 hours of the initial observation of the event. All details should be documented on the serious adverse event and death report and signed by the responsible investigator or one of the authorized staff members. In circumstances where it is not possible to submit a complete report an initial report may be made giving only the mandatory information.

The investigator will decide whether the SAE is related to the treatment (i.e. unrelated, unlikely, possible, probable, definitely and not assessable) and the decision will be recorded on the serious adverse event form. The assessment of causality is made by the investigator using the following criteria:

Relationship	Description
Unrelated	There is no evidence of any causal relationship
Unlikely	There is little evidence to suggest there is a causal relationship (e.g. the
	event did not occur within a reasonable time after administration of the trial
	medication). There is another reasonable explanation for the event.
Possible	There is some evidence to suggest a causal relationship (e.g. the event
	occurred within a reasonable time after administration of the trial medication),
	but other factors may have contributed to the event (e.g. the patients clinical
	condition, other concomitant treatments).
Probable	There is evidence to suggest a causal relationship and the influence of other
	factors is unlikely.
Definitely	There is clear evidence to suggest a causal relationship and other
	contributing factors can be ruled out.
Not	There is insufficient or incomplete evidence to make a clinical judgment of the
assessable	causal relationship.

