The investigator will report all SAEs to the sponsor without undue delay after obtaining knowledge of the events. The sponsor will report the SAEs through the web portal *ToetsingOnline* to the accredited METC that approved the protocol, within 7 of first knowledge for SAEs that result in death or are life threatening followed by a period of maximum 8 days to complete the initial preliminary report. All other SAEs will be reported within a period of maximum 15 days after the sponsor has first knowledge of the serious adverse events.

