#### 8.6 Data safety monitoring board (DSMB)

A DSMB is established to perform ongoing safety surveillance which means that (S)AEs will be monitored. The DSMB will have insight into the total number of (S)AEs and will, as needed, review individual records to be able to analyze potential associations between complications and the study protocol. The members will not have insight in the efficacy data. Accumulating data on (S)AEs will be send to the DSMB for safety review by the researchers. All members have independent positions from the trial study group. The composition and responsibilities of the DSMB are described in detail in the DSMB charter.

The advice(s) of the DSMB will only be sent to the principal investigators of the study. Should they decide not to fully implement the advice of the DSMB, they will send the advice to the reviewing METC, including a note to substantiate why (part of) the advice of the DSMB will not be followed.

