#### 4.2.1 Data safety monitoring board

A data safety monitoring board (DSMB) is installed to review the trial's progress including data quality and safety data. No interim review regarding efficacy will be performed and therefore the efficacy data can remain blinded throughout the course of the study. Safety data, consisting of serious adverse events, adverse events and suspected unexpected serious adverse events are reported directly from the researchers to the DSMB and will be unblinded. Recruitment data (e.g. data return rates, treatment compliance) will be provided to the DSMB by the research team. The DSMB will meet at least once a year. An extra meeting may be scheduled on request of the principal investigators, study coordinator or of the members of the DSMB.

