##### *Secondary end points:*

[figure not shown]
- Number of postnatal transfusions per infant  $\geq 7$  days up to 3 months of life.
- The percentage of infants requiring a postnatal transfusion up to 3 months of life;
- Time from birth to first postnatal transfusion (days);
- Hemoglobin level at first postnatal transfusion (g/dl);
- Number of days of hospitalization and readmission(s) associated with erythrocyte transfusion(s);
- Course of hemoglobin up to 3 months of life.

*Safety end points:*

- The percentage of infants with a systolic blood pressure  $\geq 2$  SD above age adjusted mean systolic blood pressure during treatment;
- The percentage of infants with ferritin levels  $>200$   $\mu\text{g/L}$  during treatment.

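### Protocol 8.2.1 makes no exception for admissions to give a top-up transfusion, so crude SAE counts would partly mirror the primary endpoint and, under SAP 4.2.1, go to the DSMB unblinded

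*Protocol*

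**What the plan says.** **What counts as serious.** Protocol 8.2.1 defines an adverse event as any unwanted experience of a trial patient, related to the drug or not. It lists "Hospitalization or prolongation of hospitalization" among the results that make an event serious. Nothing there exempts expected, disease-related or endpoint events, and the SAP adds no exemption.

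**How transfusions are described.** Protocol section 3 refers to "an average of two top-up transfusions and therefore two hospital admissions per infant", and section 5.9 costs "a clinical admission at a day-care-center for one top-up transfusion". The number of transfusions per infant up to 3 months is the primary endpoint (Protocol 5.5, SAP 4.3). Protocol 5.5 also lists "Number of days of admission for top-up transfusions" as a secondary endpoint, and SAP 4.3 keeps an equivalent one.

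**Who receives the reports.** Protocol 8.2.1 sends SAEs from the investigator to the sponsor and on to the ethics committee. Fatal and life-threatening cases have a shorter deadline, and "All other SAEs will be reported within a period of maximum 15 days". Protocol 8.6 gives the DSMB the total number of (S)AEs and says: "The members will not have insight in the efficacy data". SAP 4.2.1 says that safety data, including SAEs, "are reported directly from the researchers to the DSMB and will be unblinded". The same section expects the efficacy data to stay blinded throughout.

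**The concern.** Late anaemia that brings an infant back to hospital for a transfusion fits the definition in 8.2.1, so one admission can be both an SAE and an efficacy outcome. If EPO saves transfusions, it then also lowers the crude SAE count, whatever its safety.

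Two things are at stake. First, a crude by-arm SAE comparison would lean towards EPO and could hide a real excess of other serious events. The plan offers few other safety comparisons between arms: the named safety endpoints are blood pressure and ferritin, and SAP 4.2 schedules blood pressure for EPO-treated infants only. Second, the intended separation between the DSMB and efficacy fails if a proxy for the primary endpoint arrives by arm in the safety reports. A lesser matter is that the ethics committee would receive routine, expected care as individual SAE reports.

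**Working it through.** **Inputs.** From Protocol 5.4 and SAP 4.4: mean transfusions per infant 1.9 (standard care) and 0.8 (EPO), standard deviations 1.5 and 0.9, 21 per group, two-sided alpha 0.05, stated power 81%, drop-out 5%. SAP Table 2 is laid out for 22 per arm. The share of transfusions that would be counted as a hospitalization or prolongation is not given, so it is varied below as an assumption.

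**The plan's own figure.** The variances sum to 1.5² + 0.9² = 3.06. A normal approximation with n = 21 gives 1.1 / √(3.06/21) = 2.88, and 2.88 − 1.96 = 0.92, so power is 82%. With the Mann-Whitney efficiency factor 3/π the effective n is 20.05, which gives 80%. The stated 81% lies between the two. Simulations with assumed count distributions having these means and SDs gave 71% to 74%, but the plan's own hypothesised distribution is in a figure that is not shown. Nothing below depends on the power. For drop-out, 42/0.95 = 44.2, which the plan takes as 44, or 22 per arm.

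**Expected SAEs from transfusion admissions alone.** Number per arm × design mean × share counted:

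| Assumption | Standard care | EPO | Gap |
|---|---|---|---|
| Every transfusion counts | 22 × 1.9 = 41.8 | 22 × 0.8 = 17.6 | 24.2 |
| Three quarters count | 31.4 | 13.2 | 18.2 |
| Half count | 20.9 | 8.8 | 12.1 |
| Day care not classed as hospitalization | near 0 after discharge | near 0 after discharge | near 0 |

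In the first three rows the ratio is 0.8/1.9 = 0.42, which is the design effect on the primary endpoint.

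**Spread around the expected values.** With all transfusions counted, the approximate 95% range is n × mean ± 1.96 × SD × √n:
- Standard care: 41.8 ± 1.96 × 1.5 × √22, or 28 to 56.
- EPO: 17.6 ± 1.96 × 0.9 × √22, or 9 to 26.

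**Leaving out early transfusions.** Treatment starts at about day 7, so transfusions before then should be similar in both arms. Removing e of them per infant from each arm gives a gap of 22 × (1.9 − e) − 22 × (0.8 − e) = 24.2 for any e. With e = 0.4 (assumption) the totals are 33.0 versus 8.8. For e from 0.2 to 0.6 they run from 37.4 versus 13.2 to 28.6 versus 4.4.

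**Room to mask harm.** With every transfusion counted and other serious events otherwise equal, the EPO arm would need 24.2/22 = 1.1 extra other SAEs per infant before the crude totals looked equal. With half counted it would need 12.1/22 = 0.55.

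**Reporting load.** The two arms together give 41.8 + 17.6 = 59.4 expected reports to the ethics committee if all count, or 29.7 if half do. Over the roughly 42 months from May 2017 to October 2020 in Protocol 5.1, 59.4 is about 1.4 a month.

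**The case against.** The other side has a substantial case.

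- **The reading of 8.2.1 can be disputed.** An SAE must first be an undesirable experience, and investigators may not treat guideline care for the disease under study as one. Day care may not be classed as hospitalization, and a transfusion during the birth stay need not prolong it. This stands as a limit on size. It does not remove the point, because the protocol itself calls these visits admissions and settles none of these questions.
- **Some sorting is already required.** Every SAE form carries a causality grade, and the annual safety report (Protocol 8.3) covers suspected reactions only, so admissions judged unrelated would drop out of it. The 48-hour report is limited to deaths, life-threatening events and unexpected SAEs. But the onward route to the ethics committee covers all SAEs, and the route to the DSMB in SAP 4.2.1 has no causality filter.
- **No planned analysis uses the SAE total.** There is no test or stopping rule on it, and Table 2 has no SAE row. This stands. A reader might infer that the trial's planned safety analysis is biased. The documents do not support that: what is affected is crude counts, not a specified comparison.
- **The DSMB consequence is conditional.** A reader might infer that the DSMB will certainly learn the efficacy result, or that the error rate is compromised. Neither follows. Protocol 8.6 mentions only totals, so by-arm exposure rests on the SAP. The charter and monitoring plan are not available and may address it. Members may in any case review individual records, and no interim efficacy review is planned.
- **The reporting load is small,** at about 1.4 reports a month even if all count. This stands, and the load alone would not justify a change.

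**Conclusion.** The point holds in a limited form. Followed literally, 8.2.1 puts admissions for the primary-endpoint treatment into the SAE counts. SAP 4.2.1 then passes those counts unblinded to a board that is not meant to see efficacy. This is more than a missing detail, because the stated rule gives a worse safety comparison than one that separates the two kinds of admission.

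The size depends on what is counted: about 42 versus 18 expected if every transfusion counts, about 21 versus 9 if half do, and possibly near zero after discharge if day care is excluded. It is tempting to read 42 versus 18 as an upper limit. It is not one, since observed totals can fall on either side. The figures also assume that the design effect is true: if EPO does nothing, both arms expect about 42 and there is no imbalance.

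The DSMB part assumes that the charter contains no contrary rule. The change is worth making, but the primary result does not depend on it.

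**What to change.** 1. **Protocol 8.2.1.** State that an admission, including day care, made solely to give a top-up transfusion at the guideline haemoglobin threshold is recorded as an efficacy outcome and not as an SAE. It remains an SAE if there is a complication, a transfusion reaction, a stay prolonged for another reason, or a suspicion that the anaemia is drug-related.
2. **Name the threshold.** SAP 4.1 gives cut-offs of 10.5 g/dL (days 0–6), 8.9 g/dL (days 7–13) and 7.2 g/dL (from day 14). Protocol 5.2 also allows transfusion for symptoms at 7.2–8.8 g/dL after discharge, which SAP 4.1 lacks. Say whether that rule qualifies.
3. **SAP.** Add one descriptive by-arm table of infants with any SAE excluding transfusion admissions, with those admissions on a separate line.
4. **DSMB format.** Leave to the charter how transfusion admissions are shown to the board. Pooling them over arms should not be required, because it would hide an arm imbalance unless members asked.

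The cost is a short protocol and SAP amendment and a re-sorting of SAE records by reason for admission. Pre-transfusion haemoglobin and admission records are already collected (Protocol 6.3, SAP 4.2), and SAP 4.2 places SAP finalisation before database lock. The main downside is that an investigator who knows the allocation must judge whether an anaemia is drug-related.

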#### 4.2 Study design

Randomized controlled trial without placebo. Included neonates will be randomized at birth to treatment with EPO (intervention group) or “standard care”, with 1:1 allocation, to be randomized in varying blocks of 4 and 6, no stratification is applied. In the treatment group, EPO (darbepoetin alfa) is administered subcutaneously at a dosage of 10  $\mu\text{g}/\text{kg}$  once a week, starting at approximately day 7, for a period of 8 weeks. Treatment is administered during weekly home visits in the treatment arm after discharge from the LUMC. Concomitant therapy with folate (0.25 mg/day) is given in both groups (standard practice). Concomitant iron therapy is given if ferritin level drops below 75 microg/l (standard practice). Weekly routine measurements of complete blood counts (including hemoglobin level, hematocrit and reticulocyte count) will be performed in both groups (standard practice). EPO is discontinued if hemoglobin level is  $\geq$  13 g/dL after at least 4 weeks of treatment with EPO. In EPO treated infants, blood pressure will be measured for safety reasons at onset of treatment, after four weeks and eight weeks. Monthly measurements of liver enzymes (aspartate aminotransferase (ASAT), alanine aminotransferase (ALAT), gamma-glutamyl transferase ( $\gamma$ GT) and lactate dehydrogenase (LDH)) will also be performed in all groups (standard practice). In addition, the neonatal EPO-level will be determined at birth in both groups. The number of postnatal transfusions received during the first 3 months of life and hemoglobin levels prior to the postnatal transfusion are recorded. After initial discharge from the LUMC, postnatal transfusions are recommended to be performed when hemoglobin levels fall below aforementioned cut-off values of hemoglobin.

Because of these clearly defined guideline and hemoglobin measures, blinding of caregivers to treatment allocation and use of a placebo was not deemed necessary.

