### 5.2 Analysis of primary and secondary outcomes

The total number of postnatal transfusions per infant from birth to the end of the follow-up period, the number of postnatal transfusions per infant  $\geq 7$  days (which is at the start of intervention in the treatment group) and the number of days of additional admissions for postnatal erythrocyte transfusions will be compared between both groups using a Mann-Whitney U test. The time from birth to first postnatal transfusion will be compared between both groups using a log rank test and will be displayed using Kaplan-Meier survival curves (in this case transfusion-free survival) by treatment group. The period of follow-up in this study is 90 days and as such the end point for included infants that do not receive transfusions during this period, is 90 days in the survival analysis. The percentage of infants requiring a postnatal transfusion up to 3 months of life will be compared between both groups using a  $\chi^2$  test. The average or median number, depending on shape of distribution, of EPO injections in the treatment arm will be reported, as well as a summary of reasons to discontinue EPO treatment.

A multiple linear regression analysis will be performed to correct the association between treatment assignment and the primary outcome (number of postnatal transfusions). The following potential

confounders identified from previous research [unpublished data] are to be corrected for if, despite randomization, there is a baseline difference between the groups: type of alloimmunization, EPO-levels at birth, number of IUTs and treatment with exchange transfusion. In case of a non-normal distribution of the number of postnatal transfusions per neonate, log transformation will be applied. If the assumptions underlying linear regression are violated, or if the value zero occurs often, a Poisson regression will be fitted. If the number of postnatal transfusions per infant <7 days of life shows a difference between the two groups, a sensitivity analysis will be performed by performing the multiple linear regression analysis (or Poisson regression) with and without the transfusions administered <7 days. This will differentiate between the clinical course of early and late anemia and will evaluate more specifically the effect of EPO treatment, which is started at 7 days of age.

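### Non-serious AEs are captured passively while only EPO infants get weekly home visits, and the 48-hour SAE report has no defined window for standard-care infants

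*Protocol*

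**What the plan says.** **How AEs are found.** Protocol 8.2.1 defines an AE as "any undesirable experience occurring to a patient during a clinical trial, whether or not considered related to the investigational drug", so the definition covers both arms. The method of capture is passive: "All adverse events reported spontaneously by the patient's parents or caregivers or observed by the investigator or his staff will be recorded". Neither document describes asking about AEs on a schedule.

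**Who is seen, and how often.** SAP 4.2: "Treatment is administered during weekly home visits in the treatment arm after discharge from the LUMC". Protocol 5.2 gives the same arrangement. Both arms share weekly blood counts (Protocol 5.2 and 6.3) and outpatient follow-up to three months (Protocol 11.1 f), but SAP 5.2 notes that the weekly frequency is advised rather than required. Neither parents nor caregivers are blinded (Protocol 5.6, SAP 4.2).

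**How SAEs are reported.** Protocol 8.2.1 has two layers. The fast one, with a limit of 48 hours, is "During protocol treatment, all deaths, all SAE's that are life-threatening and any unexpected SAE must be reported to the study coordinator". The general one is "The investigator will report all SAEs to the sponsor without undue delay after obtaining knowledge of the events", followed by timed steps from sponsor to ethics committee, for example "All other SAEs will be reported within a period of maximum 15 days after the sponsor has first knowledge of the serious adverse events". The general layer has no limit by arm or by treatment period. SAP 4.2 adds that admission and outpatient records, including those from other hospitals, are collected for every included infant.

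**Follow-up and planned output.** SAP 5.2: "The period of follow-up in this study is 90 days". SAP 4.3 lists two safety end points, blood pressure and ferritin. SAP Table 2 has no row for AEs or SAEs.

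**The concern.** When AEs are picked up only if someone mentions or notices them, the number recorded depends on how often someone is there to hear or look. Here the arms differ in exactly that respect. An infant on EPO is visited at home each week after discharge; a standard-care infant is not, and may also skip a blood count after a good hemoglobin result. Parents who know that their child is receiving a study drug may also be readier to mention minor complaints. A rash, poor feeding or irritability that never reached a clinic therefore has more chances of being recorded under EPO.

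The wording of the 48-hour duty adds a separate gap. It is tied to protocol treatment, and the documents do not say what that period is for an infant allocated to standard care.

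At stake is the reading of the safety data. AEs go to the DSMB (Protocol 8.6, SAP 4.2.1), and the annual report must weigh efficacy against harm (Protocol 8.3). An excess of minor events under EPO could be a drug effect or a product of the visit schedule, and the data as collected would not show which.

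**Working it through.** The plan states no AE or SAE rate, so there is no figure of its own to reproduce on this point.

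**1. Effect of unequal contact on non-serious AEs (illustration).**

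From the documents: 8 weekly injections, home visits in the EPO arm only, weekly blood counts in both arms. Assumed: over the 8 treatment weeks the blood counts and home visits are separate contacts and all take place, giving 8 contacts for a control infant and 8 + 8 = 16 for an EPO infant. Also assumed: each contact has the same independent chance *q* that a given non-serious AE is recorded, and the true AE risk is equal in the two arms.

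Chance that the AE is recorded after *k* contacts: 1 − (1 − q)^k.

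Ratio, EPO to control: [1 − (1 − q)^16] / [1 − (1 − q)^8] = 1 + (1 − q)^8.

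| Assumed q | Control, k = 8 | EPO, k = 16 | Ratio |
|---|---|---|---|
| 2% | 14.9% | 27.6% | 1.85 |
| 5% | 33.7% | 56.0% | 1.66 |
| 10% | 57.0% | 81.5% | 1.43 |
| 20% | 83.2% | 97.2% | 1.17 |

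The ratio cannot exceed 2 under these assumptions and falls towards 1 as recording at each contact becomes more complete. With only 4 home visits, as for an infant stopped early, k is 12 against 8. The ratio is then 21.5/14.9 = 1.44 at q = 2% and 93.1/83.2 = 1.12 at q = 20%.

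**2. Span of the 48-hour duty on a literal reading.**

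Protocol 5.2 starts EPO at day 7 for 8 weeks, so the period ends at 7 + 56 = day 63. Of the 90 days in SAP 5.2:

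- before treatment: 7 days (8%);
- during treatment: 56 days (56/90 = 62%);
- after treatment: 90 − 63 = 27 days (30%).

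Counting only from first to last dose (day 7 to day 56) gives 49 days (54%). For an infant stopped after 4 weeks under the hemoglobin rule it is about 28 days (31%). For a standard-care infant the text gives nothing to compute.

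**3. Does that span decide which SAEs are known?**

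The 48-hour sentence says how quickly three kinds of SAE must reach the study coordinator. The general duty in the same section covers every SAE, in both arms, whenever the investigator learns of it. The record collection in SAP 4.2 supplies a route to that knowledge for admissions anywhere. So the percentages in step 2 describe speed of reporting. They are not fractions of SAEs captured.

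**The case against.** **SAEs.** The strongest point on the other side is that the quoted sentence governs speed, not capture. This stands in full. A reader might infer that SAE counts by arm are not comparable, or that events after the last dose are missed. The documents do not support either: the all-SAE duty and the collection of records apply to both arms throughout. A reader might also infer two errors pulling in opposite directions, extra contacts inflating EPO counts and a truncated window deflating them. With no truncation of capture, the second error is absent. Nor does the 73-hour half-life in Protocol 11.1 e help. It comes from adults with chronic kidney disease, with similar values in children aged 2 to 16 years, and it would matter only if the window decided what was captured.

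**Meaning of protocol treatment.** The Protocol summary speaks of either treatment arm, so the period could be read to include standard care. Protocol 5.2 and SAP 4.2 use treatment group or arm for EPO only. The fair criticism is that the term is undefined, not that controls are excluded.

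**Size.** Contact numbers and recording chances are assumed. Some early injections may be given before discharge, some blood counts will be skipped, and the documents do not say who makes the home visits. This stands: the ratios show what could happen and estimate nothing.

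**Consequence.** Convulsions or a serious hypersensitivity reaction leading to admission would be SAEs and should surface in both arms. Blood pressure is assessed by scheduled measurement, so it is a separate matter. With 22 infants per arm, zero events still leaves a one-sided 95% upper limit of 1 − 0.05^(1/22) = 13%, so rare harms could not be compared under any scheme. The SAP plans no AE comparison, the DSMB can look at individual records, and the DSMB charter and monitoring plan, which were not available, may say more. All this limits the point to non-serious AEs. It does not remove it, because medical records will not show a mild event at home that was never brought to a clinic.

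**Conclusion.** The concern holds in a limited form, as a cheap improvement worth making. Non-serious AE counts can be higher under EPO with no true difference, because capture is passive, allocation is known and home contact is confined to one arm. The size is unknown; a ratio of about 1.2 to 1.9 follows from 16 against 8 contacts and a 2% to 20% chance of recording at each, all of which are assumptions. The range also supposes equal attendance at blood counts in the two arms, which may fail if high hemoglobin values lead to skipped counts more often in one of them.

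The 48-hour duty is a defect of wording. Its period is undefined for standard-care infants and, read literally, leaves about days 63 to 90 outside it after a full EPO course. The effect is on promptness of reporting to the coordinator.

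**What to change.** 1. In Protocol 8.2.1, replace the reference to protocol treatment with one calendar window for both arms, from randomization to day 90, whether or when EPO is stopped, and apply the same reporting time to all infants.
2. Ask the same short set of AE questions at the routine outpatient or blood-count contacts in both arms. Where a visit is skipped or takes place at another hospital, use the contact that the research team already has with referral hospitals (SAP 4.1).
3. Add a source field to the AE form that flags events known only from a home injection visit, so that the effect of the extra contact can be examined.
4. In the SAP, add a table of AEs and SAEs by arm over that window.

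The cost is a few lines of protocol text, a short form, some table rows and some coordination with referral hospitals, whose staff may not otherwise ask trial questions. More events will be reported from the control arm, which adds work but is the purpose of the change. No new scheduled visits are needed.
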